1.5.2 Sample size for full trial (Stage 2)

If the trial is recommended to continue at Stage 2 based on DMC interim review, the full trial will need to recruit an additional 95 for each arm that continues (152 per arm in total; 456 to the complete trial). This will provide 90% power to detect a change of RR of 0.6 (50% to 30%), with one-sided alpha of 0.027 (chosen to give a 5% FWER) and has been inflated by 5% for missing outcome data. Here the power is the chance of an effective treatment passing stage 1 and being recommended after stage 2.

1.5.3 Informal interim analysis

An informal analysis will take place after 10 participants have been recruited to each arm and followed up for 14 days. No hypothesis testing will be performed, the analysis has been set out in "MATIS SAP I Dose Verification Informal Analysis ver1.0". The DMC will review the data with guidance contained in the SAP I.

1.6 Randomisation

Patients will be randomized to one of three actively recruiting trial arms, RUX, FOS or SOC. Eligible patients will be allocated using a central web-based randomisation service that uses randomisation sequences with random block sizes that are stratified by age ($<65 \text{ vs} \ge 65$) and site. If stage 2 occurs with one intervention arm stopped then the randomisation ratio will be 1:1.

1.7 Blinding

The analysis described in this SAP will be undertaken primarily by the trial statistician who will be blind to treatment assignment. The trial statistician will only see sub-group bind data throughout the trial, which means treatment assignment will be coded as group A versus group B versus group C, without knowing which treatments A, B and C refer to. Any analysis of primary efficacy outcomes at the interim analysis stage or data with the potential to unblind the trial statistician (e.g. adherence to allocated intervention) at the interim analysis will be undertaken by an independent statistician from Newcastle University. All final analysis will be undertaken by the blinded statistician who will perform the blinded analysis prior to analysis of any data with the potential to unblind, for example analysis of the adherence data. The senior statistician based in Imperial Clinical Trials Unit will hold the information to unblind the data for closed DMC discussions.

1.8 Brief description of proposed analysis

Efficacy analysis population: We will use the intention-to-treat (ITT) population which includes all randomised participants analysed in the treatment arm to which they were allocated to regardless of treatment subsequently received, multiple imputation will be used to account for any missing data such that all randomised participants are included in the final analysis. At the formal interim analysis multiple imputation will be undertaken if greater than 5% of outcome data are missing, if \leq 5% missing a complete case analysis will be undertaken.

Safety analysis population: We will include participants who received at least one dose of study medication and analysis will be according to treatment received, regardless of randomised treatment assignment.

The formal interim analysis will be conducted after 171 participants have been recruited and have completed 14 days of follow-up after randomisation. If an experimental treatment is recommended to continue an additional 95 participants will be recruited for each arm that continues and final analysis will be completed after all participants have completed 28 days of follow-up after randomisation.

Formal interim and final analyses will be carried out sub-group blind and follow the ITT principle. That is, all randomised patients will be analysed in the treatment arm to which they were allocated to regardless of treatment subsequently received, multiple imputation will be used to include all randomise participants for the final analysis, at the formal interim analysis multiple imputation will be undertaken if greater than 5% of outcome data are missing. The analysis of the serious adverse events will be undertaken on the safety population.

All regression analysis will include adjustment for age group (<65 years or ≥65 years) and site where appropriate, since these were stratification factors in the randomisation.

All confidence intervals will be presented at the 95% level.

For the formal interim analysis (stage 1) one-sided p-values \leq 0.25 will indicate that an experimental treatment should be recommended to continue to stage 2 and for the final (stage 2) analysis one-sided p-value \leq 0.027 will be interpreted as statistically significant for the primary outcome.

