#### 4.2 STATISTICAL ANALYSIS PLAN

Analysis will be on an intention to treat (ITT) population including all randomized patients, multiple imputation will be used to include participants who have missing outcome data. Comparisons for efficacy will be made between all participants randomised to the different treatment arms, irrespective of whether they received their allocated treatment ("ITT" analyses). Comparisons for safety will be made between all participants randomised to the different treatment arms who have received at least one dose of study medication. Multiple imputation makes a missing at random assumption and a sensitivity analysis around the assumptions made will be performed using controlled multiple imputation that permits exploration of a not missing at random assumption. A complete case analysis will also be performed. The primary outcome will be analysed as binary with participants categorised WHO COVID-19 Ordinal Score <5/  $\ge 5$  by 14 days.

For Stage 1 analysis (after a target recruitment of 171 participants) we will calculate the Wald test statistics from separate logistic regression models for RUX vs SOC and FOS vs SOC, adjusted for stratification variables, with 95% confidence intervals and p-values. P-values will be one-sided and judged at the 0.25 level.

If at least one intervention arm shows promise, then stage 2 will recruit a further 95 per arm (the maximum combined sample size of stages 1 and 2 is 456 patients). The stage 2 analysis will use a one-sided p-value

MATIS version 4.0 dated 2nd November 2022

IRAS: 282552 Page **27** of **57** 

threshold of 0.027. This has been chosen to control the maximum chance of recommending an ineffective treatment at 0.05.

Contamination is a potential threat in many C19 trials, as standard of care is continuously evolving, and coenrolment to ongoing trials present a real challenge if unequal enrolment occurs across arms. For participants who were co-enrolled to a trial at the same time, or prior to the randomisation to this trial, we will adjust the final analysis though covariate adjustment. For participants who were subsequently co-enrolled after randomisation, we treat this as a post-randomisation variable and undertake a supplementary analysis to adjust for this variable along with the receipt of post-randomisation rescue medication.

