Further details will be fully described in the Statistical Analysis Plan (SAP).

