#### 5.3 EXCLUSION CRITERIA

• Requiring either invasive or non-invasive ventilation including CPAP or high flow nasal oxygen at any point

MATIS version 4.0 dated 2nd November 2022

IRAS: 282552 Page **30** of **57** 

\* Clinical suspicion of COVID-19 pneumonia will be confirmed by two independent clinicians.

<sup>† Females must be either post-menopausal for at least 1 year or surgically sterile; or if female of child-bearing potential, must not be pregnant or lactating and must agree to use an acceptable method of birth control throughout the duration of the trial and for 30 days following the last dose. Acceptable methods of birth control are defined as: hormonal contraception (pill, injection or implant) used consistently for at least 30 days prior to enrolment, intrauterine device (IUD), double-barrier (ie, condom and spermicide, or condom and diaphragm), or true abstinence (when this is in line with the preferred and usual lifestyle of the subject).

<sup>‡ Male subject with a partner of childbearing potential must agree to use an appropriate double-barrier method of contraception during the time interval between administration of the first dose of study drug and 30 days following the last dose, or must agree to true abstinence (when this is in line with the preferred and usual lifestyle of the subject).

after hospital admission and before baseline not related to a pre-existing condition (e.g. obstructive sleep apnoea)

- Grade ≥ 5 severity on the WHO COVID-19 Ordinal Scale
- O₂ saturation < 90% on ≥ 60% inspired oxygen at baseline

- In the opinion of the investigator, progression to death is inevitable within the next 24 hours, irrespective of the provision of therapy
- Any medical condition or concomitant medication that in the opinion of the investigator would compromise subjects' safety or compliance with study procedures.
- Any medical condition which in the opinion of the principal investigator would compromise the scientific integrity of the study
- Known severe allergic reactions to the investigational agents
- Use of drugs within the preceding 14 days that are known to interact with any study treatment (FOS or RUX), as listed in the Summary of Product Characteristics
- Child Pugh B or C grade hepatic dysfunction
- Pregnant or breast feeding

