#### 9.2 DURATION AND MODE OF FOLLOW-UP

All randomised participants are to be followed up until death, discharge from hospital or 28 days after randomisation (whichever is sooner). It is recognised that in the setting of this trial, there may be some variability in exactly how many days after randomisation, information on disease status is collected. This is acceptable and will be taken account of in the analyses and interpretation of results, the principle being that some information about post-randomisation disease status is better than none.

Where discharge occurs before 14 days, study medication will be sent home with patient. The study team will send a pre-paid envelope to the patients to return any unused medication and empty bottles if patients are not able to attend Day 14 and Day 28 visits in person.

Where discharge occurs before 28 days, patients will be invited to return weekly for monitoring of blood tests to confirm continued recovery from illness. Where this is not possible, monitoring of clinical status will be achieved by telephone.

Longer term (up to 10 years) follow-up will be sought through linkage to electronic healthcare records and medical databases including those held by NHS Digital, Public Health England and equivalent bodies, and to relevant research databases (e.g. UK Biobank, Genomics England).

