- Requiring either invasive or non-invasive ventilation including CPAP or high flow nasal oxygen at any point after hospital admission and before baseline not related to a pre-existing condition (e.g. obstructive sleep apnoea)
- Grade \geq 5 severity on the WHO COVID-19 Ordinal Scale.
- O_2 saturation < 90% on \ge 60% inspired oxygen at baseline.
- In the opinion of the investigator, progression to death is inevitable within the next 24 hours, irrespective of the provision of therapy.
- Any medical condition or concomitant medication that in the opinion of the investigator would compromise subjects' safety or compliance with study procedures.
- Any medical condition which in the opinion of the principal investigator would compromise the scientific integrity of the study.
- Known severe allergic reactions to the investigational agents.
- Use of drugs within the preceding 14 days that are known to interact with any study treatment (FOS or RUX), as listed in the Summary of Product Characteristics.
- Child Pugh B or C grade hepatic dysfunction.
- Pregnant or breast feeding.

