We will undertake an exploratory analysis to examine the treatment effect (reported as a risk ratio (RR)) adjusted for compliance. This will be achieved through a complier adjusted case (CACE) analysis using a two-stage residual inclusion estimator (2SRI) approach with randomisation group as the instrumental variable. The primary analysis model described in 3.1.3 will be refitted with the log link function (instead of logit function) to give the treatment effect as a RR with corresponding 95% confidence interval and p-values. The CACE will then be estimated for this model and we will compare the CACE estimates of the RR to the RR obtained from the refitted primary analysis model. Randomisation meets the criteria for an adequate instrument variable since (i) randomisation predicts the treatment receipt, (ii) randomisation is unconfounded with the outcome and we assume (iii) no direct effect of randomisation on the outcome (other than via treatment receipt) – *the exclusion restriction*. After the second stage of estimation, the standard errors of the estimates will be corrected using the method of Terza. ^{9, 10}

This approach can only include adherence information in the intervention groups as the equivalent usage in the control participants is not recorded (as the control intervention is SOC and can differ between participants and is likely to evolve with time). SOC will be assumed to be 100% compliant with prescribed treatment.

We will define a complier as an individual who receives $\geq 90\%$ of prescribed dose. In addition to the analysis using a 90% threshold to define compliance we will undertake alternative analysis defining a 'complier' as an individual who receives $\geq 60\%$, $\geq 70\%$ and $\geq 80\%$ of prescribed dose to explore the impact of alternative definitions of compliance.

Analysis will adjust for baseline WHO COVID-19 score (3 or 4), age (<65 or ≥65)), receipt of known effective treatments dexamethasone and/or tociluzimab, prior vaccination against COVID-19, and receipt of paxlovid and/or molnupiravir at the time of or prior to randomisation into MATIS and site as fixed as per the primary analysis model described in section 3.1.3. The model will be modified in a similar manner as the primary outcome modelling in the event of low event rates.

iv. Time of enrolment

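### Does the safety population in SAP 1.8 leave out the standard-of-care arm?

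*SAP*

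**What the plan says.** SAP 1.8 gives two populations. Efficacy uses all randomised patients as allocated. For safety the rule is: "We will include participants who received at least one dose of study medication and analysis will be according to treatment received", irrespective of the arm assigned. The same section adds: "The analysis of the serious adverse events will be undertaken on the safety population".

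Protocol 4.2 has a similar dose condition. Its safety comparisons are between participants "randomised to the different treatment arms who have received at least one dose of study medication", and it leaves further detail to the SAP.

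SAP 2.8 specifies the SAE analysis. At both stages events are tabulated by treatment arm, with the number of patients affected and the number of events. At stage II it adds incidence rate ratios for RUX against SOC and for FOS against SOC, with 95% confidence intervals. SAP 1.4 lists SOC first among the treatment groups.

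**The concern.** The documents do not define study medication, but their usage points to the two trial drugs. The exclusion criterion in SAP 1.3.1 concerns drugs "known to interact with any study treatment (FOS or RUX), as listed in the Summary of Product Characteristics", and Protocol 5.3 carries the same criterion. Protocol 9.2 says: "Where discharge occurs before 14 days, study medication will be sent home with patient", and goes on to the return of unused supply. A patient allocated to SOC has no such supply.

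Taken literally, the rule in SAP 1.8 therefore admits no SOC patient, except one who took RUX or FOS and would be grouped under that drug. The rate ratios in SAP 2.8 would have no denominator. Safety of the two drugs is a stated secondary objective (Protocol 2.2), and the SAE analysis is the one analysis that SAP 1.8 ties to this set. A rule that could not support it would be a real fault.

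**Working it through.** No stated figure is in dispute. The check sets the population rule beside the analyses that use it and counts the patients affected.

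**1. Patients the literal rule fails to place (SAP 1.5).**

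| | All randomised | SOC | Drug arms (most the literal set can hold) |
|---|---|---|---|
| Stage 1 | 171 | 57 (57/171 = 33.3%) | 2 × 57 = 114 |
| Final, both drugs continue | 456 | 57 + 95 = 152 (152/456 = 33.3%) | 2 × 152 = 304 |
| Final, one drug stops at the planned 57 | 57 + 152 + 152 = 361 | 152 (152/361 = 42.1%) | 57 + 152 = 209 |

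SOC is one third of the final sample only if both drugs continue.

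**2. What SAP 2.8 requires.** Tables by arm and two ratios, each with SOC in the denominator. With the literal set, neither ratio exists. With SOC patients included, both do.

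**3. Readings that satisfy both sections.** Two are possible.
- The dose condition applies to the RUX and FOS arms, and SOC patients enter as SOC.
- SOC counts as study medication. This fits the usage in Protocol 9.2 less well.

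Both readings bring the SOC arm in. Under the first, all SOC patients who took neither drug enter.

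**4. Whether SAP 3.1.5 rules out the second reading.** The compliance section says that "the equivalent usage in the control participants is not recorded". That remark concerns percentage adherence, needed for the complier analysis of the primary outcome. It does not mean that receipt of SOC drugs is unknown. Protocol 7.14 requires all medications given after enrolment to be recorded on the case report form, and SAP 3.1.2 and 3.1.3 use receipt of dexamethasone and tocilizumab as covariates. The remark is not evidence that SOC patients cannot enter the set.

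**5. Grouping rule.** SAP 1.8 states one: treatment received. Protocol 4.2 refers to randomised arms but defers detail to the SAP. The two can differ only for patients who crossed over or took the wrong drug. The documents give no number of such patients, so no size can be put on the difference.

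**6. Drug-arm patients who were never dosed.** SAP 1.8 requires at least one dose, so on its wording they are out.

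**7. What else depends on the rule.** SAP 1.8 assigns the SAE analysis to the safety set and efficacy to the all-randomised set. The primary outcome, 28-day severe disease, the ordinal score, its components, time to discharge and the laboratory models in SAP 3.1 and 3.2 are planned comparisons with SOC that the dose condition does not touch.

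**The case for a change.** The strongest case for a change is that intent is not a derivation rule. Under SAP 1.7 the trial statistician sees groups coded A, B and C. Someone who does not know which group is SOC cannot informally exempt it from a dose condition. Grouping by treatment received also leaves some room to argue that a never-dosed drug-arm patient was in effect treated with SOC and belongs there, which would change the denominators. The repair would take a sentence or two in the SAP.

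Part of this stands. The clause is absent, and writing it down would cost little. The blinding argument carries less weight. Any dose condition needs dosing records, and such records by their nature identify the group that has none. SAP 1.7 provides for this: at the interim, data that could unblind go to the independent statistician, and at the end the blinded analysis is done before such data are analysed. The difficulty would be the same with the clause written in.

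On never-dosed patients, the alternative reading has to override the one condition the sentence does state. It is possible but strained, and the documents give no number of such patients from which to size an effect. An additional SAE table by randomised arm would be a matter of preference and would not correct an error.

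**Conclusion.** The observation about the text is right: neither SAP 1.8 nor Protocol 4.2 says how SOC patients enter the safety population. It does not call for a change. SAP 2.8 names SOC as the comparator, SAP 1.4 lists it as a treatment group, and applying a dose condition only to the arms that have a dose is the ordinary reading. On that reading, 57 SOC patients at stage 1 and up to 152 at the final analysis form the comparator, and every SAE table and rate ratio in SAP 2.8 can be produced as planned. The expected effect on results is nil.

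This rests on two assumptions: the analyst reads SAP 1.8 together with SAP 2.8, and never-dosed drug-arm patients are left out, as SAP 1.8 says. The separately issued SAP I was not available, but the safety population is defined in SAP 1.8 without reference to it. This is a gap in wording that analysts will fill sensibly.

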1.9 Informal interim analysis outcomes - Completed 29th Jan 2021

At the end of the initial stage, the mean CRP values over days 1, 7, 14 and 28 (adjusted for baseline) will be calculated by treatment arm. The mean CRP will also be calculated by treatment arm and visit (adjusted for baseline). These results will form part of the evidence to verify the dose and duration of treatment for the next stage. The pre-specified criteria guiding this inference are listed in full below.

- Dose continues unchanged: For each treatment arm (RUX or FOX) the dose and duration will remain unchanged if there is an absolute mean CRP decrease of approximately 25% or more compared to SOC by day 14 and judged to be maintained by day 28.
- Dose escalation or duration increase: For each treatment arm (RUX or FOX) an adjustment to the dose and duration will be discussed if the mean CRP decrease is less than approximately 25% compared to SOC by day 14.

The results were taken into consideration along with the number of SAEs and SARs and consistency of treatment effect across subgroups including renal failure, use of immunomodulators and age group. Platelet counts and neutrophil counts were also examined over time to monitor the treatment effect in renal failure patients with a dose reduction.

The Data Monitoring Committee and chief investigator, with contribution from the unblinded senior statistician and independent statistician reviewed the unblinded efficacy data and made a recommendation on the 29th January 2021 to the Trial Steering Committee to continue to the next stage maintaining existing dosing schedule.

2. Data analysis plan – data description

2.1 Recruitment and participant flow

Please see section 2.1 in SAP I. This will be undertaken for stage I and stage II

2.2 Baseline characteristics

Please see section 2.2 in SAP I. For ease of presentation median and IQRs will be removed from this analysis. This will be undertaken for stage I and stage II

2.3 Co-enrolment

Please see section 2.3 in SAP I. This will be undertaken for stage I and stage II

2.4 Standard of Care

Please see section 2.4 in SAP I. This will be undertaken for stage I and stage II

2.5 Withdrawals, loss to follow-up and other missing data

Please see section 2.5 in SAP I. This will all be undertaken for stage II, only withdrawal summaries will be prepared for Stage I.

2.6 Adherence to allocated treatment and dose summaries

Please see section 2.6 in SAP I. This will be undertaken for stage I and stage II

All analysis of adherence data at the formal interim analysis will be completed by the independent statistician in Newcastle University to ensure the trial statistician remains blind and only DMC members will see these results.

2.7 Descriptive statistics for outcome measures

The proportion of participants with the primary outcome of WHO COVID- $19 \ge 5$ by day 14 will be summarised by treatment arm and repeated for day 28. This will be undertaken for stage I and stage II.

In addition, the proportion of participants experiencing each of the components of the WHO COVID-19 severity scale score (mortality, invasive ventilation plus organ support (renal replacement therapy, ECMO or inotropic support), invasive ventilation, non-invasive ventilation including CPAP and high flow nasal oxygen) at any point up to day 14 (repeated up to day 28) will be summarised by treatment arm. This will be undertaken for stage I and stage II.

Trajectories of mean (SD) grades over time by treatment arm will also be plotted. This will be undertaken for stage II only.

Time spent at each of the components will be summarised as medians and IQRs by treatment arm. This will be undertaken for stage II only.

All stage 1 analysis of the WHO COVID-19 grades will be completed by the independent statistician in Newcastle University to ensure the trial statistician remains blind and only DMC members will see these results.

Inflammatory markers CRP, LDH, ferritin, D-dimer, and serum creatinine values will be summarised by treatment arm over time and presented as means (SD) and median (IQR). This will be undertaken for stage II

Summaries (means (SD) and median (IQR)) of length of stay will be tabulated amongst those that do not withdraw or die. This will be undertaken for stage II

